### Sub-study 3: Costing

As the goal of the costing study is descriptive and no statistical hypothesis testing will be conducted, the sample size is not based on statistical power calculations. Rather the sample size is based on concerns of feasibility and representativeness of the sample. The selected sample size is expected to lead to costing results that are representative of the costs for MAM and SAM treatment in these 30 health facilities and will be feasible to collect.

## Statistical analyses

[figure not shown]
### Main trial

All analyses will be reported as per CONSORT guidelines for randomized trials (25).

### Study accrual

We will report the numbers of participants who were randomized, received intended treatment, and were included in the analyses for primary outcomes. These numbers will be presented in the format as depicted in Figure 1 consistent with the flow diagram required for CONSORT reporting.

Figure 1. Study accrual profile for the main trial

\*Children will be included in analyses of relapse outcomes if they recovered and had at least one post-discharge visit

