We estimate a total sample size of 1080 children with SAM (360 per arm) and 1080 children with MAM (360 per arm) will provide at least 90% statistical power to demonstrate non-inferiority for each comparison, with a non-inferiority margin of 10 percentage points, assuming a recovery rate in the control of 77% (Table 4). For relapse outcomes, sample size will be smaller, and thus power will be lower, because only recovered children will be included in the analysis. All calculations assume a one-sided $\alpha = 0.05$ for non-inferiority and two-sided $\alpha = 0.05$ for superiority analyses.

Table 4. Sample size calculations

Scenarios with at least 80% power are **bolded**.

Primary outcome	Analysis type	Sample size per arm	Outcome prevalences reported in literature	Non-inferiority margin or detectable effect size	Assumption on control group outcome prevalence/means in sample size calculations	Power per comparison
Anthropometric recovery at discharge	Non-inferiority	360 MAM and 360 SAM children/arm enrolled; 306 MAM and 306 SAM children in analysis after 15% attrition	MAM recovery (with RUSF*): 73% (13); 73% (14); 85% (15) SAM recovery : 55.4% (16); 82.3% (17); 76% (18); 71% (pooled estimate from meta-analysis) (19)	10 percentage points (absolute difference)	55.4% (vs 45.4%)	85.6%
					77.0% (vs 67.0%)	90.0%
					82.3% (vs 72.3%)	96.8%
Relapse to wasting within 3-months post-discharge	Superiority	236 children/arm in analysis (assuming 77% of the 306 children recover)	Post-MAM relapse : 30% within 3 months (period prevalence) (20); 33% within 12-months (21) Post-SAM relapse : 6.8% 3-month cumulative incidence (22); 24% 2-month cumulative incidence (23); 30% within 3-months (unpublished); 2.6 episodes per child-year (unpublished); 1.3	35% relative reduction (incidence rate ratio = 0.65)	Incidence of 2.6 episodes per child-year	80.0%
					Prevalence of 30% (vs 20%)	71.0%

			episodes per child-year (unpublished)			
--	--	--	--	--	--	--

*RUSF = ready-to-use supplementary food

Study procedures

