All staff will be trained in the study procedures, in order to screen for eligibility, determine eligibility, collect informed consent, administer study products, and conduct follow up procedures in accordance with the trial protocol and SOPs. Before enrollment of the first participant, all study procedures will be piloted for 2 weeks at the study sites to check for any procedural problems, collect feedback from facility staff and communities, and implement any revisions to procedures as needed.

After informed consent is obtained, a unique participant number will be assigned to the participant. Clinical information related to the child's wasting episode, including documentation of routine medications received, child's anthropometry, and clinical status. In addition, the child's medical history and clinical presentation details will be abstracted from their medical records as documented by the study clinician, and copies of the medical records will be stored in the child's study file.

The study nurse will provide counseling on the specifics of wasting treatment as per Burkina Faso guidelines, including the schedule of visits, how to use the RUTF throughout the treatment course, and the duration of treatment. As per Burkina Faso guidelines, the caregiver will return regularly to the facility for follow-up care for their child (weekly for SAM; bi-weekly for MAM), during which they will receive clinical exam to assess morbidity, measurement of anthropometry, and receive another 7-day supply of RUTF. The nurse will answer any questions the caregivers might have. Adherence will be assessed at these follow up visits through caregiver report.

When the child meets the criteria for discharge, children will be counseled to return to the facility for post-discharge follow up monthly for 3 months. At these post-discharge follow-up visits, caregivers will be asked about any admissions to hospital for wasting in the previous month, and the child will be screened for wasting. More details on data collection are given in the following section and in Table 7.

Anthropometric and clinical procedures

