### Study design

#### Main trial

This will be a facility-based, triple blinded individually randomized controlled trial with three arms, including two interventions and one control arm, with a 1:1:1 allocation ratio. Children will be enrolled upon initiation of MAM or SAM treatment and followed monthly for 3 months post-discharge from treatment.

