## Study outcomes

### Main trial

The primary and secondary outcomes for the main trial and their definitions are listed in Table 1. Outcomes are the same for MAM and SAM children.

*Table 1. Primary and secondary efficacy outcomes*

Outcomes	Definition	Type of analysis
Primary outcomes		
Anthropometric recovery at discharge	WLZ $\geq$ -2 and MUAC $\geq$ 125 mm and absence of bilateral pitting edema for two consecutive visits, at the day of end of treatment	Non-inferiority
Relapse to wasting within 3 months post-discharge	A new episode of wasting (defined as WLZ/WHZ $<$ -2 or MUAC $<$ 125 mm or presence of bilateral pitting edema) within the 3-month period following recovery from the index wasting episode, among children who recovered from their index episode	Superiority
Length of stay (LOS) among recovered children	The number of days between the day the child is admitted to treatment and the day the child is determined to be recovered and thus discharged from treatment	Non-inferiority
Weight gain	Change in child's weight (gram/kilogram/day) between weight on day of admission to treatment and the day of end of treatment	Non-inferiority
Anthropometry at discharge from treatment	WLZ/WHZ, MUAC, weight, height/length, LAZ/HAZ and WAZ at the day of end of treatment	Non-inferiority
Anthropometry at 3-months post-discharge	WLZ/WHZ, MUAC, weight, height/length, LAZ/HAZ and WAZ at 3-months post-discharge (3 months after the day of end of treatment)	Superiority
Hemoglobin at discharge	Hemoglobin concentration (grams/liter) at the day of end of treatment	Non-inferiority
Hemoglobin at 3-months post-discharge	Hemoglobin concentration (grams/liter) at 3-months post-discharge (3 months after the day of end of treatment)	Superiority
Secondary outcomes		
Default from treatment	Child is absent for two consecutive visits, declared a defaulter on the second visit	Non-inferiority

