## Statistical methods

We will conduct two separate comparisons between (i) the control group and SMS-RUTF, and (ii) between the control group and S-RUTF. All analyses will be done separately by wasting severity status (MAM vs SAM); that is, all analyses will be conducted and presented among MAM children and among SAM children separately. No adjustments for multiple comparisons will be made.

For binary outcomes, we will use log-binomial regression to estimate relative risks (RRs) and 95% confidence intervals (CIs) for the RRs, adjusting for any baseline factors as appropriate (described further below). If the regression model is adjusted, we will present both crude (unadjusted) and adjusted model results. If the models do not converge, we will use Poisson regression models with robust estimation of standard errors (26) and report which model was used. Non-inferiority will be declared if the lower bound of a one-sided 95% CI for the RR lies entirely below the non-inferiority margin of a relative 12.5%. For superiority analyses, we will use a two-sided 95% CI and superiority will be declared if the lower bound of the 95% CI for the relative risk is above 1.0. All analyses will be adjusted for health center to reflect the stratified randomization (27–29).

For continuous outcomes measured at one timepoint, we will use linear regression to estimate differences in that outcome between treatment arms, adjusting for any baseline factors as appropriate and health center (as explained above). Both unadjusted and adjusted model results will be presented.

For any outcome for which non-inferiority is demonstrated, we will then sequentially test for superiority. In these cases, we will report both non-inferiority and superiority results. The superiority analysis will be considered exploratory, as the study power calculations were based on non-inferiority effect size.

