## Treatment of missing data

Wherever more than 10% of outcome observations are missing, we will report the number of observations used in the analysis. No imputation of missing data will be done, given the limited number of covariates available to predict missing observations. Every effort will be made to minimize attrition of study participants, thus keeping missing data to a minimum. Default from treatment will be considered a treatment outcome, rather than missing data.

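### The SAP does not say how a recovered child lost after month 1 or 2 counts in the 3-month relapse analysis, and the planned model takes no account of time at risk

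*SAP*

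**What the plan says.** SAP Table 1 defines relapse as a new wasting episode "within the 3-month period following recovery from the index wasting episode, among children who recovered from their index episode". Children are "followed monthly for 3 months post-discharge from treatment" (SAP, Study design, Main trial). At those visits, according to Protocol, Study procedures, "caregivers will be asked about any admissions to hospital for wasting in the previous month, and the child will be screened for wasting".

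The footnote to Figure 1 in SAP, Study accrual sets the analysis population: "Children will be included in analyses of relapse outcomes if they recovered and had at least one post-discharge visit". The shell table for the data safety and monitoring board (SAP Table 7) puts 3-month relapse under the same denominator.

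SAP, Statistical methods gives the model: "For binary outcomes, we will use log-binomial regression to estimate relative risks (RRs) and 95% confidence intervals (CIs) for the RRs". Robust Poisson regression is the fallback if the model does not converge. No offset, censoring or person-time is mentioned. Under Treatment of missing data: "No imputation of missing data will be done, given the limited number of covariates available to predict missing observations".

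The single sensitivity analysis concerns children switched to standard product near its expiry. Adherence for the complier analysis means attendance at treatment visits. Neither deals with loss after discharge.

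**The concern.** A child may be seen well at month 1 and never again. That child meets the inclusion rule, although two thirds of the risk window was not observed. The model needs a 0 or a 1 and nothing is imputed, so 0 is the value most likely to be entered.

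Relapse is a primary outcome tested for superiority. Counting unobserved months as relapse-free lowers the estimated risk in every arm. If attendance after discharge differs between arms, it also shifts the relative risk.

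**Working it through.** **Inputs from the documents.** Control relapse 30% at 3 months, 236 children per arm, two-sided alpha 0.05, and 30% vs 20% with stated power 71.0% (Protocol Table 4). Three monthly visits (SAP, Study design).

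**Assumptions.** Constant monthly hazard; loss unrelated to relapse; the loss patterns below; a lost child without observed relapse coded as not relapsed. Loss of a% + b% means a% last seen at month 1 and b% last seen at month 2.

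**1. The plan's own power.** The mean proportion is 0.25. The standard error is √(2 × 0.25 × 0.75/236) = 0.03986 under the null and √((0.21 + 0.16)/236) = 0.03960 under the alternative. Power = Φ((0.10 − 1.96 × 0.03986)/0.03960) = Φ(0.552) = 71.0%. This reproduces the stated figure.

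**2. Risk observable at each visit.** By month 1: 1 − 0.7^(1/3) = 11.2%. By month 2: 1 − 0.7^(2/3) = 21.2%. So 18.8 percentage points of risk go uncounted for each child last seen at month 1, and 8.8 for each last seen at month 2.

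**3. Equal loss in both arms.** Observed risk = f1 × 0.1121 + f2 × 0.2116 + (1 − f1 − f2) × 0.30, where f1 and f2 are the shares last seen at months 1 and 2.
- At 10% + 10%: 0.0112 + 0.0212 + 0.2400 = 27.2%.
- For a true 20% arm the month-1 and month-2 risks are 7.2% and 13.8%, so the observed risk is 0.0072 + 0.0138 + 0.1600 = 18.1%.
- RR = 0.181/0.272 = 0.664, against a true 0.667. Power by the step 1 formula falls from 71.0% to 66.0%.

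**4. Unequal loss, true risk 30% in both arms.** Control loses 5% + 5%: 0.0056 + 0.0106 + 0.2700 = 28.6%. The chance of a false benefit is the chance that the 95% interval lies wholly below 1, that is Φ(−1.96 − ln RR/SE), with SE = √((1 − pC)/(236 pC) + (1 − pT)/(236 pT)).

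| Intervention loss | Observed risk | RR | SE of ln RR | False benefit (nominal 2.5%) |
|---|---|---|---|---|
| 10% + 5% | 27.7% | 0.967 | 0.147 | 4.2% |
| 15% + 15% | 25.9% | 0.903 | 0.151 | 9.9% |

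Swapping the arms gives RR 1.03 and 1.11, so greater loss in the control arm would hide a real benefit. With 6.8%, the lowest 3-month relapse figure in the documents, the first two ratios become 0.965 and 0.896. The RR bias therefore depends little on the assumed risk.

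**5. A tempting repair that fails.** Suppose the binary analysis is limited to children with an observed relapse or a completed month-3 visit. It keeps relapsers from the lost group and drops its non-relapsers.
- At 10% + 10% loss: 0.2724/(0.2724 + 0.80 × 0.70) = 32.7%, not 30%.
- At 15% + 15% vs 5% + 5%: 0.2586/(0.2586 + 0.49) = 34.5% against 0.2862/(0.2862 + 0.63) = 31.2%, RR 1.11 with no true effect.

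**The case against.** The coding is inferred, not written. The missing-data section allows for missing outcome observations and will report the number analysed when more than 10% are missing. An included child could therefore still have a missing relapse value. This stands: the defect is an unstated rule, with one reading more natural than the others.

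A reader might infer that every child seen only once is affected. That goes too far. If the single visit is at month 3, status at the end of the window is known. Some relapses may also come to light outside scheduled visits: the gut-health sub-study samples stool on relapse, and caregivers report hospital admissions. Caregiver recall, however, covers only admissions in the previous month.

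A reader might also infer that the plan is biased towards the new products. The documents do not support this. They give no post-discharge loss by arm, they plan for 15% attrition, and they describe a blinded trial in identical packaging. The SAP does concede that taste and appearance may defeat participant blinding, so unequal attendance is possible. The ratio of 0.90 needs 30% partial loss in one arm and 10% in the other. With the worse arm at 15% it is 0.967.

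Finally, one relapse power scenario in Protocol Table 4 is a rate ("Incidence of 2.6 episodes per child-year"), which may suggest that the SAP abandoned a time-at-risk analysis. It did not: the Protocol's Statistical analysis section already specifies log-binomial regression for binary outcomes.

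**Conclusion.** The concern holds as a gap in specification with a better method at hand, and it should be fixed. The SAP combines an inclusion rule of at least one visit with a 3-month binary outcome, no time at risk and no imputation. It leaves open the status of a child lost relapse-free after month 1 or 2.

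If such children count as not relapsed, equal loss of 10% + 10% turns a 30% risk into 27.2% and lowers power from 71.0% to 66.0%, while the RR hardly moves. Unequal loss biases the RR in whichever direction the imbalance runs: about 0.97 for a modest imbalance and 0.90 for a large one.

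These sizes rest on the inferred coding, a constant hazard, loss unrelated to relapse, and assumed loss patterns. They show what could happen; they do not predict it. Benefit here means RR below 1. The SAP's superiority criterion is worded in the opposite direction, which is a separate matter.

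**What to change.** - Keep the inclusion rule of at least one post-discharge visit.
- As the main relapse analysis, use discrete-time regression on the monthly visits (complementary log-log link) or person-time regression, adjusted for health center. Censor each child without relapse at the last attended post-discharge visit.
- Report the model-based 3-month risk in each arm and the risk ratio.
- State that censoring is assumed non-informative, and report month-3 follow-up completeness by arm so that readers can judge this.
- Keep the planned log-binomial analysis as supportive, with the coding of incompletely followed children written out.
- Do not use the binary analysis restricted to an observed relapse or a completed month-3 visit, because it overstates risk.

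The cost is SAP wording and a model change. The monthly visits that it needs are already planned, and the SAP keeps the letter codes from the study team until analysis is completed, so the change can be made blind. The downside is that the fitted effect is a hazard or rate ratio unless it is converted to a 3-month risk ratio.

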## Statistical methods

We will conduct two separate comparisons between (i) the control group and SMS-RUTF, and (ii) between the control group and S-RUTF. All analyses will be done separately by wasting severity status (MAM vs SAM); that is, all analyses will be conducted and presented among MAM children and among SAM children separately. No adjustments for multiple comparisons will be made.

For binary outcomes, we will use log-binomial regression to estimate relative risks (RRs) and 95% confidence intervals (CIs) for the RRs, adjusting for any baseline factors as appropriate (described further below). If the regression model is adjusted, we will present both crude (unadjusted) and adjusted model results. If the models do not converge, we will use Poisson regression models with robust estimation of standard errors (26) and report which model was used. Non-inferiority will be declared if the lower bound of a one-sided 95% CI for the RR lies entirely below the non-inferiority margin of a relative 12.5%. For superiority analyses, we will use a two-sided 95% CI and superiority will be declared if the lower bound of the 95% CI for the relative risk is above 1.0. All analyses will be adjusted for health center to reflect the stratified randomization (27–29).

For continuous outcomes measured at one timepoint, we will use linear regression to estimate differences in that outcome between treatment arms, adjusting for any baseline factors as appropriate and health center (as explained above). Both unadjusted and adjusted model results will be presented.

For any outcome for which non-inferiority is demonstrated, we will then sequentially test for superiority. In these cases, we will report both non-inferiority and superiority results. The superiority analysis will be considered exploratory, as the study power calculations were based on non-inferiority effect size.

We will conduct one sensitivity analysis. There were children enrolled near the end of the study whose product was switched to standard of care product during their treatment course because the expiration date of the study products occurred during their treatment course. That is, they received the study product to which they were randomized for the majority of their treatment course, and then when the expiration date of that product neared, they received a standard of care product for the remainder of their treatment duration. As these children received both the study and standard of care products, including them in the study arm to which they were randomized represents misclassification and their inclusion could bias the results to the null. If we were to exclude only the children assigned to the expiring product, there is the potential to induce bias by excluding children with long treatment durations or poorer treatment outcomes in one treatment arm, making treatment outcomes spuriously appear worse in this arm. Therefore, we will conduct a sensitivity analysis excluding all children in all treatment arms who received product on or after the date on which this switch was made.

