Transfer to inpatient treatment	Referral or admission to hospital for inpatient treatment during the treatment course. As per the Burkina Faso national protocol, children are to be transferred to inpatient care if they meet any of the following criteria: negative appetite test, weight loss for 3 consecutive visits, stagnant weight for 4 consecutive visits if all other social and nutritional reasons have been addressed, onset of clinical condition (edema, fever, hypothermia, severe dehydration, repeated or incessant vomiting, severe respiratory problem, very pale with difficulty breathing, severe malaria,	Non-inferiority

	abscesses or extensive skin lesions, weakness or unconsciousness, convulsions or malaise) (4).	
Non-response to treatment	Any of the following criteria are met: Absence of weight gain after 5 weeks or at the third visit; weight loss for more than 4 weeks in the program or at the second visit; loss of more than 5% of body weight compared to admission weight at any time; or anthropometric recovery criteria not met after 3 months of follow-up in CMAM. Children who are non-responders are referred to inpatient care as per Burkina Faso guidelines.	Non-inferiority
Adherence to treatment services	Caregiver attends the recommended schedule of visits and receive RUTF supply	Non-inferiority
Relapse to SAM	A new episode of SAM (WLZ/WHZ < -3 or MUAC < 115 mm or presence of bilateral pitting edema) within the 3-month period following recovery from the index wasting episode	Superiority
Relapse to MAM	A new episode of MAM (WLZ/WHZ < -2 and $\geq$ -3, or MUAC < 125 mm and $\geq$ 115 mm) within the 3-month period following recovery from the index wasting episode	Superiority
Morbidity signs or diagnoses	Indication of morbidity on health center card	Non-inferiority
Anemia at discharge	Hemoglobin concentration < 105 gram/liter for children 6-23 months of age or < 110 gram/liter for children 24-59 months of age, at discharge	Non-inferiority
Anemia at 3-months post-discharge	Hemoglobin concentration < 105 gram/liter for children 6-23 months of age or < 110 gram/liter for children 24-59 months of age, at 3-months post-discharge	Superiority
Mortality	Death at any time during treatment or during the post-discharge follow-up period	Non-inferiority

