### Sample size and statistical power

#### Main trial

We estimate a total sample size of 1080 children with SAM (360 per arm) and 1080 children with MAM (360 per arm) will provide sufficient statistical power to demonstrate non-inferiority for each comparison, with a non-inferiority margin of relative 12.5%, assuming a recovery rate in the control of 76% and a loss to follow up of 15% (Table 4). The sample size will be smaller for analyses of relapse, because only recovered children will be included in the analysis. All calculations assume a one-sided  $\alpha = 0.05$  for non-inferiority and two-sided  $\alpha = 0.05$  for superiority analyses,  $\beta = 0.8$ , and 15% attrition. While the key objectives of this research are to evaluate effects of the alternative RUTFs on recovery and relapse, we consider as primary outcomes any outcome for which we have adequate power for clinically or policy meaningful effect sizes (5).

 Stata commands `ssi` for continuous outcomes and `artbin` for binary outcomes were used for non-inferiority analyses, and `power twomeans` for continuous outcomes and `power twoproportions` for binary outcomes were used for superiority analyses. Outcome proportions, means, or standard deviations were taken from relevant studies in literature as delineated in Table 4.

Table 4. Calculations of detectable effect sizes for all outcomes

Outcome	Outcome prevalence in the literature	Type of analysis	Non-inferiority margin (relative) with $\geq 80\%$ power (Non-inferiority)	Detectable effect size at 80% power (Superiority)	Rank of outcome
Anthropometric recovery at discharge	MAM recovery (with RUSF*): 73% (6); 73% (7); 85% (8)  SAM recovery: 55.4% (9); 82.3% (10); 76% (11); 71% (pooled estimate from meta-analysis) (12)	Non-inferiority	12.5% relative margin		Primary
Relapse to wasting within 3-months post-discharge	Post-MAM relapse: 30% within 3 months (13); 33% within 12-months (14)  Post-SAM relapse: 6.8% 3-month cumulative incidence (15); 24% 2-month cumulative incidence (16); 30% within 3-months (unpublished)	Superiority		Risk difference of 11%; Relative risk = 0.72	Primary
Length of stay (LOS) among recovered children	MAM: 36.4 days (SD 50.4 days)(17); 5.9 weeks (95% CI: 4.9, 7.0)(18) SAM: 56 days (assumed 41 day SD) (9)	Non-inferiority	MAM: 4.9 days; 12.5% relative margin SAM: 8 days; 12.5% relative margin		Primary

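### The only non-inferiority rule for binary outcomes tests the lower RR bound, which cannot rule out an unacceptable rise in default, transfer, non-response, morbidity, anemia or death

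*SAP*

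**What the plan says.** SAP, Statistical methods, sets the scope: "For binary outcomes, we will use log-binomial regression to estimate relative risks (RRs") with confidence intervals. It then gives one decision rule, that non-inferiority is declared if "the lower bound of a one-sided 95% CI for the RR lies entirely below the non-inferiority margin" of a relative 12.5%. The Protocol's Statistical analysis section has the same rule.

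SAP Table 1 types these binary outcomes as non-inferiority: recovery, adherence, default ("Child is absent for two consecutive visits, declared a defaulter on the second visit"), transfer to inpatient care, non-response, morbidity, anemia at discharge and mortality ("Death at any time during treatment or during the post-discharge follow-up period"). For the last six, more events is worse.

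Neither document defines which arm is the numerator of the RR, changes the bound for adverse outcomes, recodes them, or says whether a relative 12.5% means 0.875 or 1.125. SAP Table 4 lists other margins for five of the six (17.5% to 70%) and leaves rate and margin blank for mortality, which it ranks exploratory. It gives no bound or direction, and the decision rule does not refer to it. The one clue to orientation is its relapse row, "Risk difference of 11%; Relative risk = 0.72", where a beneficial effect is an RR below 1, that is, intervention over control.

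**The concern.** Non-inferiority on an adverse outcome means that the data exclude an increase larger than the margin. The largest increase still compatible with the data is the upper confidence bound. A lower bound below 1.125 shows only that harm beyond the margin has not been proven, and small or noisy data meet that easily.

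The word *below* is also wrong for recovery, where the lower bound should lie above 1 minus the margin. An editor who mends that word alone would leave the six adverse outcomes with a rule that rewards harm. At stake are the trial's efficacy-table statements on tolerability and safety of two new products.

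**Working it through.** **Inputs.** SAP, Sample size: "1080 children with SAM (360 per arm) and 1080 children with MAM (360 per arm"). Protocol Table 4: 306 per arm analysed after 15% attrition. Alpha: "one-sided $\alpha = 0.05$ for non-inferiority", so z = 1.645. Control risks and margins: SAP Table 4. RR = intervention/control.

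**The plan's own figure.** The SAP claims at least 80% power for recovery at 76% with a 12.5% relative margin (0.125 × 76 = 9.5 points). SE = √(2 × 0.76 × 0.24/306) = 0.0345; power = Φ(0.095/0.0345 − 1.645) = Φ(1.11) = 86.6% on the risk-difference scale, or 90.2% on the log-RR scale. The claim holds. That calculation assumes the correct rule. With the rule as worded and a margin of 0.875, an equal product passes 9.8% and a product at the margin 95%.

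**Formula.** SE(log RR) = √[(1−p0)/(306·p0) + (1−p1)/(306·p1)].
- P(lower bound < c) = Φ[(ln c − ln RR)/SE + 1.645]
- P(upper bound < c) = Φ[(ln c − ln RR)/SE − 1.645]

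**One row in full: SAM default, 8.5%, true RR 1.5 (12.75%).** SE = √(0.0352 + 0.0224) = 0.240.
- Lower bound < 1.125: Φ(−0.288/0.240 + 1.645) = Φ(0.446) = 67% (simulation 68%).
- Lower bound > 0.875: 1 − Φ(−0.539/0.240 + 1.645) = 1 − Φ(−0.602) = 73%.
- Upper bound < 1.125: Φ(−2.84) = 0.2%. Upper bound < 1.45 (Table 4): Φ(−1.79) = 3.7%.

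As a single data set: 39/306 against 26/306 gives RR 1.50 with one-sided bounds 1.01 and 2.23. The lower bound is below 1.125 and also above 0.875, so both wordings pass it. The upper bound exceeds both 1.125 and 1.45.

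**Margin read as 1.125: percentage of trials declared non-inferior (simulated; formula agrees within about 2 points)**

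| Outcome (control risk; Table 4 margin) | RR 1.125 | RR at Table 4 margin | RR 1.5 | RR 2 |
|---|---|---|---|---|
| Default MAM (6.8%; 50%) | 95 | 72 | 72 | 25 |
| Default SAM (8.5%; 45%) | 95 | 73 | 68 | 16 |
| Transfer MAM (5.8%; 70%) | 95 | 59 | 75–76 | 32 |
| Transfer SAM (20.1%; 40%) | 95 | 56 | 35 | <1 |
| Non-response MAM (32.2% or 28%; 30%) | 95 | 62–67 | 11–18 | <1 |
| Non-response SAM (12.5%; 25%) | 95 | 87 | 56 | 5 |
| Morbidity (61.1%, 60.0%; 17.5%) | 95 | 82 | <1 | not possible |
| Anemia (49%, 51%; 17.5%) | 95 | 86 | <1 | <1 or not possible |

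The 95% column is exact by construction: when the true RR equals c, the formula reduces to Φ(1.645).

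**Margin read as 0.875, with *below*.** At RR 1.125, default passes 75–78%, transfer 51–81%, non-response 28–67%, anemia 4–6% and morbidity under 1%.

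***Below* changed to *above* 0.875.** SAM default passes 12–13% at RR 1, 25% at 1.125, 73% at 1.5 and 98% at 2; SAM transfer passes 98–99% at 1.5. The pass rate rises with harm.

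**Mortality.** The documents give no rate. Assuming 1–3% in the control arm, lower bound < 1.125 passes a doubling of risk in 57–87% of trials.

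**Upper bound against 1 + Table 4 margin.** The pass rate is 5% at the margin. At RR 1.5 it is 4–5% for default, 2% for SAM transfer and 11% for MAM transfer, whose margin allows 1.70. Power at RR 1: default 39–40%, transfer 49–67%, non-response 27–72%, anemia 62–65%, morbidity 79–80%. With a blanket 12.5% margin, power at RR 1 would be 10–57%.

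**The case against.** **Orientation is not defined.** The superiority rule in the same paragraph (lower bound above 1.0) makes sense for relapse only with control over intervention. On that orientation the lower bound is the right one for adverse outcomes, and changing *below* to *above* 0.875 would cap harm. This stands as a reason to define the RR. It does not rescue the rule: the relapse RR of 0.72 points the other way, *below* is wrong on either orientation, and a control-over-intervention RR would put recovery on the wrong bound.

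**The size depends on an unstated margin.** This also stands. The 95% figure belongs to the 1.125 reading; on the 0.875 reading morbidity and anemia rarely pass at RR 1.125.

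**Other protections exist.** SAP Table 4 ranks these outcomes secondary and mortality exploratory. RRs with confidence intervals will be estimated, and the DSMB receives deaths, referrals, transfers and adverse events by arm without any non-inferiority label. A harmful estimate would therefore be visible. That limits the consequence, but the declared conclusion would still contradict the interval printed beside it.

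**A stronger reading is tempting:** that a product raising default, transfer or death by half or more would usually be called non-inferior. The documents do not support it. At RR 1.5 it is true of default, MAM transfer and, narrowly, SAM non-response, but not of SAM transfer (35%), MAM non-response (11–18%), morbidity or anemia. At RR 2 it fails for every outcome with a stated rate. For death it rests on an assumed rate.

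**Conclusion.** The defect is in the text: one lower-bound rule covers six outcomes for which only an upper bound can exclude harm. Under the 1.125 reading, a product with a true RR of 1.125 is declared non-inferior about 95% of the time rather than 5%, and a product at its own Table 4 margin 56–87% of the time. The error is greatest for modest harms and rarer events, and shrinks as harm grows.

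These figures assume RR = intervention/control, 306 analysed per arm, Table 4 control risks, unadjusted Wald bounds on log RR, and no effect of the health-center adjustment. The SAP counts default as an outcome rather than missing data, so its denominator could approach 360. SAM default at RR 1.5 would then pass about 63% (SE = 0.240 × √(306/360) = 0.221; Φ(−0.288/0.221 + 1.645) = Φ(0.34)), and the 95% at RR 1.125 would not change.

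**What to change.** In SAP Statistical methods and Protocol Statistical analysis:

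1. Define RR as intervention over control.
2. For default, transfer, non-response, morbidity and anemia at discharge, declare non-inferiority if the upper bound of the one-sided 95% CI is below 1 + the outcome's margin.
3. For recovery and adherence, require the lower bound to be above 1 − the margin.
4. State that the outcome-specific margins in SAP Table 4 govern, and that 12.5% applies only where that table lists it. Confirm that the row labelled compliance is the adherence outcome of Table 1.
5. Report mortality with counts, risk difference and 95% CI, and make no non-inferiority claim. Setting a margin is the alternative, but the documents offer no rate on which to base one.
6. Align the superiority rule with the same RR, so that benefit on relapse is an upper bound below 1.0.

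This changes wording, not data collection. The cost is fewer secondary outcomes declared non-inferior: with the Table 4 margins, power at equality is about 27–80% at 306 per arm, so many rows fall short of the 80% in that table's heading. That is the information the trial actually has on these outcomes, and the report should say so.
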